3.2 Eligibility Criteria

The inclusion criteria are: 1) adult men or women ages 18-50 years; 2) closed or low grade open (Gustilo type I or II) tibial or femoral shaft fracture;²⁴ 3) fracture treated with a reamed, locked, intramedullary nail; 4) acute fracture (enrolled within 7 days of injury); and 5) provision of informed consent. Fifty years was selected as the upper age limit to minimize potential confounding with post-menopausal endocrine changes that affect bone metabolism. For the purposes of the study, femoral shaft fractures will be defined as any injury in which the majority of fracture line is distal to the lesser trochanter and proximal to the distal metaphyseal flare of the femoral condyles (**Figure 1**). Intertrochanteric extension or distal articular extension is permitted. Similarly, a tibial shaft fracture will be defined as an injury with a primary fracture line between the proximal meta-diaphyseal flare to the distal metaphyseal region ending one joint width proximal to the tibial plafond (**Figure 2**). Intra-articular extension is permitted.

The exclusion criteria are: 1) osteoporosis; 2) stress fractures; 3) elevated serum calcium (>10.5 mg/dL); 4) atypical femur fractures as defined by American Society for Bone and Mineral Research (ASBMR) criteria;²⁵ 5) pathological fractures secondary to neoplasm or other bone lesion; 6) patients with known or likely undiagnosed disorders of bone metabolism such as Paget's disease, osteomalacia, osteopetrosis, osteogenesis imperfecta etc.; 7) patients with hyperhomocysteinemia; 8) patients with an allergy to vitamin D or another contraindication to being prescribed vitamin D; 9) patients currently taking an over the counter multivitamin that contains vitamin D and are unable or unwilling to discontinue its use for this study; 10) patients who will likely have problems, in the judgment of the investigators, with maintaining follow-up; 11) pregnancy; 12) patients who are incarcerated; 13) patients who are not expected to survive their injuries; and 14) other lower extremity injuries that prevent bilateral full weight-bearing by 6 weeks post-fracture.

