3.5.4 Potential adverse events associated with vitamin D

A recent systematic review comprehensively examined the effectiveness and safety of vitamin D supplementation among all ages of adult fracture patients.²⁷ The majority of research has been performed in elderly fracture populations; however, the safety of a wide range of doses is well established. Studies with doses of 4,000 IU daily and loading doses from 50,000 IU for up to 7 days or single loading doses up to 500,000 IU have been used without complication.²⁹

Since vitamin D regulates PTH and serum calcium levels, it is theoretically possible that vitamin D supplementation could lead to hypercalcemia. Of the 1,088 patients included in the systematic review, 4 cases of hypercalcemia were reported (0.4%).³⁰ Furthermore, there have been no cases of hypercalcemia in several high loading dose clinical trials. Regardless, we will monitor serum calcium levels at enrolment, 6 weeks, and 3 months post-fracture, and clinical signs of hypercalcemia will be sought at all clinical encounters. If hypercalcemia is identified, participants will be instructed to stop their vitamin D supplementation immediately and the hypercalcemia will be treated as indicated.

Finally, we will monitor for increased falls among the study participants. While we do not expect to observe this adverse event (AE) in our 18 to 50 year-old adult population, a recent study of 200 elderly fracture patients found that a 60,000 IU monthly loading dose and 24,000 IU monthly loading dose plus 300 µg of calcifediol were associated with increased falls compared to the control group.³¹ This single study contradicts several other high loading dose clinical trials, and these concerns have not been borne out of the healthy adult fracture population. This may be a result of the fact that supplementation in the non-osteoporotic fracture population has not been extensively studied (highlighting the need for the proposed research), or because these concerns regarding the risk of falls do not apply to healthy adults without osteoporosis.

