3.7.5 Analysis of blood samples

Serum calcium testing will be performed by the hospital laboratory and will be part of the unblinded medical chart for patient safety. The remainder of serum samples (PTH, 25(OH)D, PINP, CTX) will be analyzed in a blinded manner at the end of the study. Laboratory personnel at the University of Maryland's Muscle Research Laboratory will process the samples for storage in the -80° C freezer. Upon completion of all blood work for the study, the serum samples will be transferred to the Institute for Clinical and Translational Research Clinical Research Unit Core Laboratory to be analyzed as a single batch to eliminate inter-batch assay variability. The results of the analyses will be sent to the CEO to be added to the REDCap study database and included within the final data analysis. The treating surgeon will remain blinded to these results. Participants may request the results of their blood analysis at the end of the study.

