4.2.3 Other Secondary Outcomes

All other secondary outcomes will be presented using point estimates and appropriate measures of variance to describe supplementation adherence, participant safety, and key aspects of participant compliance with the protocol (**Table 4**). Supplement adherence will be summarized using means and 95% confidence intervals for participant self-reporting and the mean cumulative dose taken at 3 months. The incidence of AEs and re-operations for fracture healing complications in each group will be described with counts and proportions. Serum levels of calcium and PTH will be summarized using means and 95% CIs. Participant compliance with the protocol will be summarized descriptively with counts and proportions.

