To determine the effect of low amounts of vitamin D₃ supplementation on fracture healing at 3 months	Low daily dose will increase healing compared to placebo. While the low daily dose is not expected to increase circulating vitamin D as rapidly as the high dose strategies, this comparison will determine if rapid serum increases are necessary to improve fracture healing.	1. FIXIT (Clinical)	Comparisons between the low daily dose & placebo groups will be made using an Independent t-test (alpha=0.20)*
		2. RUST (Radiographic)	
		3. PINP (Biologic)	
		4. CTX (Biologic)	

*Using Phase II screening trial approach, comparisons are non-definitive and an increased alpha level has been adopted.

Table 3: Secondary Outcome Analysis

Objective	Hypothesis	Fracture Healing Outcome	Method of Analysis
To determine if 25(OH)D serum levels are associated with fracture healing at 3 months	There will be an association between fracture healing and: 1) patients' enrolment serum 25(OH)D, 2) their change in 25(OH)D from enrolment to 3 months, 3) their 25(OH)D level at 3 months	1. FIXIT (Clinical)	Associations will be quantified using Univariate Analysis (alpha=0.20)*.
		2. RUST (Radiographic)	
		3. PINP (Biologic)	
		4. CTX (Biologic)	

*Using Phase II screening trial approach, comparisons are non-definitive and an increased alpha level has been adopted.

[figure not shown]
[figure not shown]
[figure not shown]
Table 4: Other Secondary Outcomes Analysis

Objective	Hypothesis	Outcome	Method of Analysis
Supplementation adherence	Daily vitamin D ₃ adherence will be <80% and loading dose vitamin D ₃ adherence will be >95%	Self-report	Summary statistics of means and confidence interval.
		Count of pills	
Participant safety	Adverse events will be rare across all 4 treatment groups.	Adverse event	Summary statistics of proportions.
	Re-operations for a composite of fracture healing complications will follow the same 3 hypotheses as fracture healing.	Re-operations for a composite of fracture healing complications	Summary statistics of proportions.
	Levels of serum calcium will be similar across the 4 treatment groups. Levels of serum calcium will be within normal reference ranges.	Serum Calcium	Summary statistics of means and confidence interval.
	Levels of serum PTH will be similar across the 4 treatment groups. Levels of serum PTH will be within normal reference ranges.	Serum PTH	Summary statistics of means and confidence interval.

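### Calcium and PTH are summarised only by group means with 95% CIs, which does not show whether participants' levels stay within the reference ranges, as Table 4 hypothesises

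*Combined protocol and SAP*

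**What the plan says.** Section 4.2.3 gives the whole analysis of the two laboratory safety measures in one sentence: "Serum levels of calcium and PTH will be summarized using means and 95% CIs". Table 4 repeats this as summary statistics of means and confidence intervals. In the same rows Table 4 sets out the expectations: levels similar across the four groups, and also "Levels of serum calcium will be within normal reference ranges" and "Levels of serum PTH will be within normal reference ranges". No count or proportion out of range, no maximum and no shift table is planned.

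The documents give no reference range for PTH. The only calcium figure is an exclusion criterion in Section 3.2, "elevated serum calcium (>10.5 mg/dL". No threshold is given for hypercalcemia during follow-up.

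Participant-level handling is described elsewhere. Section 3.5.4 says "we will monitor serum calcium levels at enrolment, 6 weeks, and 3 months post-fracture", adds that clinical signs will be looked for at every encounter, and continues: "If hypercalcemia is identified, participants will be instructed to stop their vitamin D supplementation immediately". Section 3.7.5 says "Serum calcium testing will be performed by the hospital laboratory and will be part of the unblinded medical chart for patient safety", whereas "The remainder of serum samples (PTH, 25(OH)D, PINP, CTX) will be analyzed in a blinded manner at the end of the study".

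**The concern.** A reference range is normally applied to one person's value. A group mean can sit in the middle of the range while some members of the group are outside it, so the planned summary does not answer the question that Table 4 raises if that question is about participants.

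The adverse event table might fill the gap, but the documents do not ensure that it does. Sections 3.7.3 and 6.5.1 define an adverse event by symptoms, signs, illness or experience and do not name laboratory values. Section 3.7.3 then presents calcium and PTH as something monitored besides adverse events. A high calcium without symptoms may or may not be counted, and without a stated threshold that depends on judgement. For PTH the route is closed in practice, because results first exist after the final batch assay.

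At stake is the usefulness of the safety report. Section 1.0 names dosing safety in this population as a research need, and Section 3.5.4 states its own benchmark for hypercalcemia as a proportion of patients. Followed to the letter, the plan need not produce a figure comparable with that benchmark.

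**Working it through.** **Arm size.** Section 4.1 gives a difference of 2, SD 3, and alpha and beta of 0.20. Sidedness is not stated; two-sided reproduces the plan's figure:

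n = 2 × (1.2816 + 0.8416)² × 3² / 2² = 20.3, rounded up to 21 per group. Then 21 / 0.9 = 23.3, rounded up to 24, and 4 × 24 = 96. All three match the plan and are not in dispute. Each mean therefore rests on about 21 to 24 participants.

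**What a mean with its CI can miss.** The following are assumptions, not figures from the documents: unaffected participants have mean 9.4 mg/dL and SD 0.3 to 0.5, and affected participants are at 11.5 mg/dL. The comparison value of 10.5 mg/dL is the enrolment limit in Section 3.2, used only because no other is given.

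With 2 of 24 affected and SD 0.4:
- Mean = (22 × 9.4 + 2 × 11.5) / 24 = 9.575.
- Sum of squares = 21 × 0.4² + 22 × (9.4 − 9.575)² + 2 × (11.5 − 9.575)² = 3.360 + 0.674 + 7.411 = 11.445.
- SD = √(11.445 / 23) = 0.705.
- 95% CI = 9.575 ± 2.069 × 0.705 / √24 = 9.28 to 9.87.

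The same calculation over the assumed range, for an arm of 24:

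| Affected | Mean | CI, SD 0.3 | CI, SD 0.4 | CI, SD 0.5 |
|---|---|---|---|---|
| 1 (4.2%) | 9.49 | 9.27 to 9.71 | 9.24 to 9.73 | 9.21 to 9.76 |
| 2 (8.3%) | 9.58 | 9.30 to 9.85 | 9.28 to 9.87 | 9.25 to 9.90 |
| 3 (12.5%) | 9.66 | 9.34 to 9.98 | 9.32 to 10.00 | 9.30 to 10.02 |
| 6 (25%) | 9.93 | 9.52 to 10.33 | 9.51 to 10.34 | 9.49 to 10.36 |

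Every interval lies below 10.5. With 21 per arm and 6 affected, the highest upper limit is 10.48, still below.

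**How likely a case is.** Section 3.5.4 reports 4 of 1,088, or 0.368%.
- Any case in an arm of 24: 1 − (1 − 4/1,088)²⁴ = 8.5%.
- Two or more in an arm of 24: 8.46% − 24 × (4/1,088) × (1 − 4/1,088)²³ = 8.46% − 8.11% = about 0.35%.
- Any case among 96: 1 − (1 − 4/1,088)⁹⁶ = 29.8%.

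**What counts would show.** Exact two-sided 95% limits:
- 0/24: upper limit 1 − 0.025^(1/24) = 14.2%.
- 1/24: 4.2% (0.1% to 21.1%).
- 3/24: 12.5% (2.7% to 32.4%).
- 0/21: upper limit 16.1%.
- 0/96: upper limit 3.8%.

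Even an arm with no cases leaves considerable uncertainty, which a mean does not convey.

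**The case against.** The strongest reply is that the plan already deals with hypercalcemia where it matters. Calcium is measured three times per participant, the result is in the chart at once, and the protocol attaches an action for that participant. Section 3.5.4 discusses hypercalcemia under potential adverse events, and a high value can be read as a sign. A case that led to stopping supplementation would then probably be recorded and appear in the per-group counts. This stands as far as it goes. A reader might infer that the plan hides individual hypercalcemia; the documents do not support that. What remains is that counting a symptom-free value is left open, and that the argument does not extend to PTH.

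Second, Section 4.2.3 is openly descriptive. A reader might infer that the plan sets up a hypothesis that it cannot test, but no formal test is intended for these outcomes. The neighbouring expectation of similarity across groups is also a group-level statement, so the reference-range statement could be read in the same way. A mean with a CI would address that reading, although the ranges to compare it with would still be missing.

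Third, the illustration is far from the documented rate. Two of 24 (8.3%) is about 22 times 0.37% (8.33 / 0.368 = 22.7). That is fair. The rate comes from mixed regimens across all ages of adult fracture patients, so it does not settle the risk in these arms, but nothing in the documents points to a rate as high as the one illustrated.

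**Conclusion.** The point holds as a minor reporting gap. The only planned summary of calcium and PTH levels does not show whether participants are within the reference ranges, and the adverse event table does not reliably supply that information: it is ambiguous for calcium and in practice unavailable for PTH.

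Under the assumed calcium values, up to a quarter of an arm of 24 could exceed 10.5 mg/dL while the CI for the mean stays below it. This rests on affected participants being at 11.5 mg/dL; much higher values would move the interval. It demonstrates what the summary can miss and does not predict that cases will occur.

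Two stronger readings should be set aside. A reader might infer that the choice of a Phase III dose would be compromised, but no selection rule in the documents depends on calcium; the stated link to the Phase III control group, in Section 3.5.2, is preliminary efficacy. A reader might also take 10.5 mg/dL as the protocol's definition of hypercalcemia in follow-up, but it is documented only as an enrolment exclusion.

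**What to change.** Keep the means and 95% CIs. In Section 4.2.3 and Table 4, add for each arm, at 6 weeks, at 3 months and at any post-baseline visit, the number and proportion of participants with calcium outside the laboratory reference range, and the same for PTH. Give exact 95% CIs, the maximum value, and as denominator the participants with a result.

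State the reference ranges used for both measures, since none is given for PTH and the calcium limit in Section 3.2 serves eligibility only. State also whether an out-of-range calcium without symptoms is counted in the adverse event table, so that the two tables can be read together.

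The cost is a few table rows and two sentences of text. Table 1 already schedules both measurements at baseline, 6 weeks and 3 months, so no new data are needed, and design, sample size and participant care are unchanged.

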4.2.4 As Treated Sensitivity Analyses

The specific aim and the relevant other secondary outcome analyses will be repeated following as-treated analyses. These sensitivity analyses will be completed after the above outcome analyses have been completed and once unblinding has occurred. As treated will be defined as participants who received both loading doses of vitamin D and participants who did not miss 20 or more daily doses of vitamin D. Therefore, participants who missed a loading dose of vitamin D and participants who missed 20 or more daily doses of vitamin D will not be included in the as-treated sensitivity analyses.

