2.4 Hypotheses for the Primary and Secondary Objectives

Primary Objective: Lower extremity shaft fractures heal via callus formation and secondary bone healing. This seminal process begins within a few weeks of injury and vitamin D metabolites have been extensively implicated in this stage of healing. During these early weeks, circulating vitamin D levels are most likely to be critical to bone healing; therefore, we hypothesize:

- 1) *High doses (loading or daily) will increase healing compared to low daily dose.* Using high doses will rapidly increase the circulating vitamin D available during fracture callus formation.
- 2) *High loading dose increases healing compared to high daily dose.* Loading doses will overcome medication adherence issues and increase circulating vitamin D even more rapidly than daily doses.
- 3) *Low daily dose will increase healing compared to placebo.* While the low daily dose is not expected to increase circulating vitamin D as rapidly as the high dose strategies, this comparison will determine if rapid serum increases are necessary to improve fracture healing.

Secondary Objective: Based on experimental data and the role of vitamin D on bone metabolism, a correlation between circulating vitamin D levels and fracture healing is expected; however, the efficacy of various supplementation strategies may be dependent on the patient's baseline vitamin D status or other related changes. For example, it is known that the dose response of supplementation varies depending on the patient's serum 25(OH)D levels, with larger increases seen in patients with serum levels <20ng/ml.

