3.4 Randomization Methods

Each participant will be randomized to 1 of 4 treatment groups: 1) 150,000 IU loading dose vitamin D₃ plus daily dose placebo; 2) loading dose placebo plus 4,000 IU vitamin D₃ per day; 3) loading dose placebo plus 600 IU vitamin D₃ per day; or 4) loading dose placebo plus daily dose placebo. The daily vitamin D₃ supplements/placebo will be provided in a blinded manner. The daily treatment will commence within 1 week of injury and will be taken for 3 months. The loading dose vitamin D₃ supplements/placebo will be given within 1 week of injury and at 6 weeks (+/- 2 weeks) post-injury.

Allocation to the 4 study groups will be concealed using a centralized 24-hour computerized randomization system that will allow internet-based allocation. The treatment allocation will be stratified on the following prognostic factors to ensure balance between the intervention groups: fracture type (closed vs. open) and long bone fracture (tibia vs. femur).

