3.5 Vitamin D₃ (Cholecalciferol) Treatment Groups

3.5.1 Blinded administration

The loading dose of 150,000 IU will consist of 3 50,000 IU capsules of vitamin D₃. The loading dose placebo will consist of 3 capsules that are identical to the 50,000 IU capsules with no active ingredient. The loading dose vitamin D₃ supplements/placebo will be given within 1 week of injury and at 6 weeks (+/- 2weeks) post-injury while in hospital or at the outpatient fracture clinic.

The daily vitamin D₃ supplements/placebo will be provided in a blinded manner and the daily treatment will commence within 1 week of injury. The daily doses (4,000 IU, 600 IU, and placebo) will be identical and will be comprised of one capsule. Patients will be given a bottle of either active vitamin D₃ or placebo capsules and will be instructed to take one capsule daily for 3 months. The placebo capsules will have no active ingredients and will be identical to the vitamin D capsules. To measure supplementation adherence, participants will be asked to bring their bottles to their follow-up visits. At the 3-month visit, participants will return their bottle to the clinical research coordinator. If the participant does not return the bottle, the clinical research coordinator will provide them with an envelope to return it via mail.

All doses of vitamin D and placebo will be obtained from Bio-Tech Pharmacal, Inc. (Fayetteville, AK). The unblinding protocol can be found in **Figure 3**. Following the completion of the study, participants may be unblinded their treatment group upon request.

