3.7.3 Other secondary outcomes

The other secondary outcomes will include assessing supplementation adherence between daily and loading doses, confirming participant safety as measured by AEs and serum levels of calcium and parathyroid hormone (PTH), and assessing protocol adherence (e.g. completion of outcome assessment and participant follow-up).

Adherence with vitamin D supplementation will be assessed by participant self-report, by counting the tablets for the daily doses at each follow-up, and by direct observation for the loading doses.

Participant safety will be assessed by AEs, defined as any symptom, sign, illness, or experience that develops or worsens in severity during the course of this study. Within the AEs collected, fracture healing complications will be identified, and will include nonunion (defined as failure of the fracture to progress towards healing for 2 consecutive months and at least 6 months post-fracture), delayed union (defined as a failure of progression of fracture healing beyond the expected median healing time of 4 months with pain at the fracture site), hardware failure (defined as broken or bent nail or locking screw),³³ wound healing problems (previously published criteria by Anglen 2005), and infection (superficial and deep as defined by Centers for Disease Control and Prevention (CDC) criteria). Wound healing problems and infection are a part of the composite fracture healing complication outcome because previous animal and infectious disease clinical research has suggested that vitamin D can improve wound healing and reduce infections.³⁴⁻³⁷ In addition to AEs, serum levels of calcium and PTH will be monitored and we will record results of the participants' pre-operative metabolic profile. These data will be used to understand the baseline metabolic health of the participants and will be used as needed in the event of suspected AEs.

Participant adherence with the protocol will be assessed by monitoring the completion of outcome measures, including clinic assessments (FIX-IT), radiographs (RUST), and blood work (CTX, PINP, 25(OH)D, calcium, and PTH), documentation of AEs and re-operations, and completion of follow-up to 12 months.

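### The 'as-treated' set in Section 4.2.4 is a non-adherer exclusion whose vitamin D dose criteria leave the placebo arm undefined and wrong-arm recipients unplaced

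*Combined protocol and SAP*

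**What the plan says.** Section 4.2 makes intention-to-treat the principle for all outcome analyses and adds as-treated sensitivity analyses. Section 4.2.4 repeats the specific-aim analyses, which are the three hypotheses of Section 2.4, and the relevant other secondary outcomes in this set. The set consists of "participants who received both loading doses of vitamin D and participants who did not miss 20 or more daily doses of vitamin D". Participants who fall short on either count "will not be included in the as-treated sensitivity analyses". The work is done after the main analyses and "once unblinding has occurred".

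Section 3.4 describes four double-dummy arms. Arm 1 has active loading doses and placebo daily capsules. Arms 2 and 3 have placebo loading doses and active daily capsules (4,000 IU or 600 IU). Arm 4 is "loading dose placebo plus daily dose placebo".

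Section 3.8 foresees that a participant may receive the wrong arm and keeps that person in the study. Table 4 expects daily adherence below 80% and loading-dose adherence above 95%.

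**The concern.** There are two problems.

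- **The label and the rule do not match.** An as-treated analysis groups people by what they took. This rule only removes people, so it is a per-protocol exclusion, and the participants for whom an as-treated analysis is chiefly useful, those given the wrong arm, have no stated place in it.
- **The criteria do not fit the arms.** They count doses of vitamin D, yet every arm has at least one dummy component and the placebo arm has two. The third hypothesis (low daily dose versus placebo, H3 below) is the one exposed. Its placebo side may be empty, unfiltered, or filtered like the low-dose side, depending on how the words are read.

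As scheduled, the analyst would settle this after the main results and the allocation are known. If placebo stays whole while low dose is filtered on adherence, a departure from the intention-to-treat result could reflect unequal selection and not treatment.

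**Working it through.** **1. The wording applied arm by arm**

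| Arm | Active loading | Active daily | Inclusion sentence, active doses, either route | Exclusion sentence, active doses | All capsules counted |
|---|---|---|---|---|---|
| 1 Loading | yes | no | judged on two loading doses | same | both checks |
| 2 and 3 Daily | no | yes | judged on daily doses | same | both checks |
| 4 Placebo | no | no | admits nobody | removes nobody | both checks |

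The two sentences of Section 4.2.4 disagree only about arm 4, the comparator for H3.

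**2. The plan's own sample size** (Section 4.1: difference 2, SD 3, α = β = 0.20)

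n = 2 × 3² × (1.2816 + 0.8416)² / 2² = 20.3, so 21 per group. Then 21 / 0.90 = 23.3, so 24 per group and 96 in total. This agrees with the plan. A one-sided α would give 13, so two-sided 0.20 is used below.

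**3. Does the cut-off bite?** Three months is taken as about 90 daily capsules. Missing 20 leaves 70/90 = 77.8% adherence (76% to 78% for 84 to 92 days). Mean adherence of 80% already means 18 missed. The cut-off therefore lies close to the adherence that Table 4 expects.

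**4. Share retained (assumed).** The documents give no distribution. With beta-distributed adherence, the share missing fewer than 20 of 90 is:

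| Mean adherence | SD 15 points | SD 20 | SD 25 |
|---|---|---|---|
| 70% | 0.344 | 0.419 | 0.478 |
| 75% | 0.489 | 0.535 | 0.577 |
| 80% | 0.631 | 0.648 | 0.676 |

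The range is about 0.34 to 0.68, or 7 to 14 of 21.

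**5. Shift in H3 if only low dose is filtered.** Assume no drug effect, FIX-IT SD 3, and correlation r between adherence and healing (not in the documents). With k the share kept and c the normal point with upper tail k:

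shift = 3 × r × φ(c) / k

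- k = 0.68, r = 0.3: 3 × 0.3 × 0.358 / 0.68 = 0.47 points towards low dose.
- k = 0.34, r = 0.3: 3 × 0.3 × 0.366 / 0.34 = 0.97 points towards low dose.
- r = −0.3 (for example, if those who heal well stop their capsules): the same sizes towards placebo.
- r = 0: no shift.

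**6. Rejection rate.** Simulated t-tests at two-sided 0.20, 21 per arm before filtering, 20,000 trials per setting. At r = 0.3 the rate is 0.245 (k = 0.68) and 0.313 (k = 0.34); by symmetry the two-sided rate is the same at r = −0.3. At r = 0 it is 0.196-0.199. With the same filter in both arms, and adherence distributed alike in both, the shift is within 0.01 points and the rate is 0.195-0.206.

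**7. Power left after a common filter** (noncentral t, 2 points, SD 3, two-sided 0.20): 0.804 at 21 per arm, 0.676 at 14, 0.476 at 7.

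**The case against.** The strongest reply is that all study capsules are meant. Section 3.7.3 says "Adherence with vitamin D supplementation will be assessed by participant self-report, by counting the tablets for the daily doses at each follow-up"; this is done while allocation is blinded, so placebo capsules must be counted too. Section 3.5.4 says that, if hypercalcemia is found, "participants will be instructed to stop their vitamin D supplementation immediately", whatever the arm. On that reading H3 is filtered alike on both sides and the bias disappears. The reading is plausible but not settled: where the protocol means both products it can say so, as in Section 3.5.1, where the loading dose "supplements/placebo will be given within 1 week of injury". Section 4.2.4 does not.

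A reader might go further and infer that nobody in any arm qualifies, because no arm has active product by both routes. Section 4.2.4 itself repeats all the specific-aim comparisons, so that cannot be the intention. Nor does the timing after unblinding prove an active-dose rule. Grouping by product received would need unblinding too, and the clause may simply put this work after the main analyses.

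It is also fair to say that the label is partly terminology, since the exclusions are spelled out, and that wrong-arm receipt is mentioned only as an example, with no frequency from which to size it. What stands is that the text does not choose between a filtered and an unfiltered placebo arm, and gives wrong-arm recipients no group.

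**Conclusion.** The point holds as a low-severity defect of definition. It affects a sensitivity analysis only; the intention-to-treat results are unaffected and no stated decision rule uses this set.

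The size is conditional. On the unfiltered-placebo reading, with 34-68% of the low-dose arm kept and a correlation of plus or minus 0.3, H3 moves by about 0.5-1.0 FIX-IT points and two-sided rejection is about 0.25-0.31 against 0.20. Retention and correlation are both assumptions. At zero correlation, or if all capsules count, there is no shift.

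Two stronger inferences are not supported. One is that the set favours low dose: the documents give no adherence-healing correlation, and a negative one reverses the direction. The other is that the choice of Phase III control is compromised: Section 3.5.2 links that choice to low dose versus placebo, but not to this set.

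**What to change.** Amend Section 4.2.4 before unblinding:

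- Rename the set per-protocol.
- Define adherence on the assigned study capsules, active or placebo, by one rule in all four arms: both loading administrations taken and fewer than 20 daily capsules missed.
- Determine missed daily capsules by pill count, using self-report only where the count is missing.
- Report the number retained per arm.
- If the name as-treated is kept, group participants, including wrong-arm recipients, by the product they actually received.

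The change costs wording only, because Section 3.7.3 already collects the adherence data. The price is smaller sets: about 7-14 per arm under the assumed adherence, with power for 2 points of about 0.48-0.68 in 1:1 comparisons. The common rule also removes some loading-arm participants who took both active doses but missed dummy capsules. This affects the first two hypotheses, and the second rests on the premise that "Loading doses will overcome medication adherence issues", so it should be stated as a limitation. Filtering each arm on its active component alone would avoid that loss but would bring back unequal filtering, so I would not add it. Any such set is selected after randomisation and can only support the intention-to-treat result.
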